Group	Number of Trial Participants	Maximum number of staff who provided assessment for that participant	Fleiss's kappa	95% Confidence Interval
Participants	47	N/A	0.69	0.39 to 0.98
Doctor performing caesarean section	26	2	0.24	-0.22 to 0.71
Midwife or doctor receiving baby at birth	32	3	0.44	0.09 to 0.80
Endocrinologist with participant contact between treatment administration and birth	33	2	0.33	-0.01 to 0.67
Midwife or doctor caring for mother and / or baby in the ward	15	4	0.43	-0.10 to 0.96
Research midwife collecting outcome data	45	2	0.81	0.54 to 1.00
Midwife administering (or checking) trial medication	41	4	0.84	0.68 to 1.00

Fleiss's Kappa Interpretation: <0 Poor agreement between the predicted allocation and the true allocation; 0.01-0.20 Slight agreement; 0.21-0.40 Fair agreement; 0.41-0.60 Moderate agreement; 0.61-0.80 Substantial agreement; 0.81-1.00 Almost perfect agreement. N/A – not applicable

Current International Guidelines

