Neonatal care for all infants will be in accordance with local protocols for the management of infants born to women with diabetes. At a minimum, all infants will undergo blood glucose testing (preferably using a glucose oxidase method (eg i-STAT or blood gas analyser) within the first 2 hours of life and then every 3-4 hours until 3 consecutive blood glucose recordings $>2.6\text{mmol/L}$. Further management including the treatment of hypoglycaemia and the timing of subsequent blood glucose measurements will be determined according to the local site algorithms. Where a site does not have a local algorithm, we recommend that Australian sites follow the Safer Care Victoria algorithm (Appendix 3) and New Zealand sites follow the Auckland DHB algorithm (Appendix 4)

Concomitant Medications / Treatments: All concomitant medications received by both the mother following randomisation, and the infant following birth, up until the time of discharge home following birth will be recorded. There are no restrictions regarding concomitant medications except antenatal corticosteroids (which constitute an exclusion criterion if received at any time before randomisation).

Compliance: Compliance with the allocated treatment schedule will be recorded, however as analysis will be by intention to treat, non-compliance with the allocated treatment schedule (including failure to complete the two injections) will not be regarded as an indication for exclusion or withdrawal from the trial.

Assessment of Blinding: The ability to retain blinding will be assessed in a subset of the participants if required (see section 7.4 Trial Risks). The following participant staff groups will be asked to predict which group the participant was allocated to (Betamethasone or Placebo or uncertain).

and their reason for this

- Participants
- Any staff members providing care for the participant or her baby
- Research staff involved in collection of outcome data

Data Collection: Prior to discharge following birth, participants will be asked by the site research team to complete a questionnaire about any side effects following trial medication administration. This will include questions regarding a range of symptoms including pain at the site of injection, flushing, fatigue, nausea, headaches, visual changes, changes in fetal movement patterns, hyperglycaemia, hypoglycaemia and adjustments to insulin doses.

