7.4 TRIAL RISKS

Trial Risk One: Potential for unblinding of participants and staff

We will collect data regarding whether participants, clinicians and research staff remain blinded to the treatment allocation for a subset of participants. These data will only be collected in the event of (i) slow recruitment (see Trial Risk 2) or (ii) projected budget shortfalls (see Trial Risk 3). Data will be analysed prior to completion of the trial to determine whether the trial should pivot to an open label trial (ie betamethasone would be prescribed on site for participants allocated to betamethasone and participants, clinicians and research staff would be aware of the treatment allocation). The decision to pivot to an open trial will be made by the Trial Steering Committee if the Kappa statistic for participants, postnatal clinicians or research staff is above 0.41 (indicating moderate agreement between the participant, clinician or research staff and the true treatment allocation). Regardless of the success of blinding in the perinatal period, children would be assessed for outcomes in later childhood by health professionals who are unaware of their treatment group allocation; it is the later childhood outcomes that will be critical in determining the balance between risks and benefits of ACS.

Trial Risk Two: Slow recruitment

Given the pace of change in obstetric and neonatal practice, it is important that this trial is completed in a timely manner – with recruitment to be completed within the 5 year time frame. We will review recruitment progress every 6 months to consider strategies to improve recruitment. Recruitment targets will be established by the Trial Steering Committee at the time of activation of the first recruiting site(s). If recruitment is less than 80% of the expected target at 2 consecutive timepoints, the trial steering committee will consider the need to analyse the blinding assessment data (described in Trial Risk One) to determine whether the trial should pivot to an open label trial to allow a greater number of sites to participate.

Trial Risk Three: Budget shortfalls

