8.2 STATISTICAL METHODS TO BE UNDERTAKEN

We will undertake descriptive statistical analysis reporting the proportion of women screened, eligible, approached, consented and refused as well as the time taken to complete study procedures.

Outcomes will be compared between the intervention and control groups using an intention-to-treat analysis. For all binary outcomes the magnitude of the between-group differences will be quantified by fitting a logistic regression model to estimate the odds ratio (OR) and 95% confidence interval (CI) for the corresponding population OR, stratified by recruitment site, type of diabetes (Type 1 diabetes, Type 2 Diabetes, Gestational Diabetes), and gestation at planned elective CS (35⁺⁰ to 36⁺⁶ weeks, 37⁺⁰ to 38⁺⁶ and 39⁺⁰ to 39⁺⁶ weeks). Linear regression will be used for non-categorical outcomes. For infant outcomes models will be fitted using Generalised Estimating Equations to allow for non-independence of outcomes among twins from the same pregnancy.

Assessment of blinding will be undertaken using Kappa statistic to assess the correlation between the participant or staff members "guess" of the allocation and the true allocation.

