8.3 INTERIM ANALYSES

If recruitment falls below 80% of the expected recruitment rate after two consecutive 6 monthly assessments, we will undertake a detailed assessment of research staff at participating sites to understand barriers and facilitators to recruitment. We will also commence the collection of data regarding the ability to maintain blinding for a minimum of 6 months (or until a minimum of 100 participants if fewer than 100 participants have been recruited in 6 months) to undertake an analysis of the potential to maintain blinding. If the blinding of participants indicates that there is at least moderate agreement between the participants prediction of the allocation and their true allocation (Fleiss's Kappa statistic is above 0.41), the Trial steering committee will recommend reverting to an "Open label trial" where the use of placebo is abandoned and

participants will be allocated to either “Open Label Betamethasone” (ie the participant, research staff and clinical staff will be aware of the patients allocation) or “standard care” without the use of either betamethasone or a placebo. An open label trial will allow additional sites to participate and substantially reduce the cost and logistics of the supply of masked betamethasone and normal saline syringes.

There are no other planned interim analyses for this trial. In particular, there will be no interim analyses based on the primary outcome. The Data and Safety Monitoring Committees may recommend an interim analysis if concerns are raised about the safety or benefit to risk profile of the trial.

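### The kappa cut-off of 0.41 that can end the use of placebo is poorly suited to three-way guesses: how 'uncertain' answers are counted can decide the result

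*Protocol*

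**What the plan says.** - **The statistic.** Protocol 8.2: "Assessment of blinding will be undertaken using Kappa statistic to assess the correlation between the participant or staff members" guess and the true allocation. No type of kappa is named there.
- **The trigger in 8.3.** The Trial Steering Committee will recommend an open-label design if there is "at least moderate agreement between the participants prediction of the allocation and their true allocation (Fleiss's Kappa statistic is above 0.41". This covers participants' guesses only.
- **The trigger in 7.4 (Trial Risk One).** The committee decides on the change "if the Kappa statistic for participants, postnatal clinicians or research staff is above 0.41". The type of kappa is not named, and three groups count instead of one.
- **The answers.** Under Assessment of Blinding in 5.1, respondents are asked to "predict which group the participant was allocated to (Betamethasone or Placebo or uncertain". Those asked include "Any staff members providing care for the participant or her baby", so one participant can have several staff guesses.
- **The pilot.** Table 2 in 3.2 reports Fleiss's kappa by group, with a column headed "Maximum number of staff who provided assessment for that participant" that runs from 2 to 4 for staff and is not applicable for participants. Its footnote reads the statistic as predicted against true allocation; the lowest band is "Poor agreement between the predicted allocation and the true allocation".

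No section says how 'uncertain' enters the kappa, or how several staff guesses on one participant are combined with the truth.

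**The concern.** The cut-off governs a change of design from placebo-controlled to open label, so it should give one answer for one set of data. Three features of kappa work against that here.

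1. The guess has three categories and the truth has two. If 'uncertain' is kept, those answers can never agree with the truth and kappa falls. If they are dropped, kappa describes only those who ventured a guess.
2. Kappa gives one number for both arms. Section 3.2 reports that pilot guesses leaned on maternal hyperglycaemia, a consequence of the active drug, so unblinding may differ by arm.
3. Fleiss's kappa is built for interchangeable raters. If the truth is entered as one rater among several staff, pairs of staff who agree with each other raise the value whether or not they are right.

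At stake is whether placebo is given up, or kept, because of a coding choice made after the guesses are in.

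**Working it through.** **The plan's own figure.** Table 2 gives participants a Fleiss's kappa of 0.69 (95% CI 0.39 to 0.98, n = 47). The raw guesses are not given, so this cannot be rebuilt. With Fleiss's null standard error, 47 two-category guesses give an interval of about 0.40 to 0.98. Forty-five definite guesses with 7 wrong give 0.686 (0.39 to 0.98). That would fit two uncertain answers having been dropped, but does not prove it.

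**'Uncertain' answers (reaches the participant rule in 8.3).** Let u be the share uncertain and a the accuracy among those who guess, both equal across arms, with 1:1 allocation (5.1). Neither u nor a is given in the documents. The assumed range for a is 0.70 to 0.95.

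- Dropped: kappa = 2a − 1.
- Kept as a third category (Fleiss): Po = (1 − u)a, Pe = (2 − u)²/8 + u²/4, kappa = (Po − Pe)/(1 − Pe).
- Correct minus wrong, over all asked: (1 − u)(2a − 1).

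Example with u = 0.20 and a = 0.80: Po = 0.64 and Pe = 0.405 + 0.010 = 0.415, so the kept value is 0.225/0.585 = 0.385.

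| Per 100: correct / wrong / uncertain | Dropped | Kept (Fleiss) | Correct minus wrong over all |
|---|---|---|---|
| 64 / 16 / 20 | 0.60 | 0.385 | 0.48 |
| 60 / 10 / 30 | 0.71 | 0.35 | 0.50 |
| 76 / 14 / 10 | 0.69 | 0.56 | 0.62 |
| 60 / 0 / 40 | 1.00 | 0.375 | 0.60 |

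The first, second and fourth rows cross 0.41 on the coding of 'uncertain' alone. In the fourth, the type of kappa matters too: Cohen's gives (0.60 − 0.30)/(1 − 0.30) = 0.43 against Fleiss's 0.375. The third row, near pilot accuracy with 10% uncertain, does not cross.

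Share uncertain at which the kept-category Fleiss value falls to 0.41:

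| Accuracy a | 0.75 | 0.80 | 0.845 (2a − 1 = 0.69, the pilot value) | 0.90 | 0.95 |
|---|---|---|---|---|---|
| u | 9.5% | 17.5% | 23% | 29% | 34% |

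At a = 0.70 the dropped value is already 0.40, so no handling crosses.

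**Pooling of the arms.** As an illustrative extreme, everyone on betamethasone guesses correctly and everyone on placebo answers 'uncertain'. Then Po = 0.50. The average category shares are 0.50, 0.25 and 0.25, so Pe = 0.25 + 0.0625 + 0.0625 = 0.375. Fleiss's kappa = 0.125/0.625 = 0.20, at the top of the slight band in Table 2, although one arm is fully unblinded. With 'uncertain' dropped, kappa is 0/0. The per-arm index is 1.0 and 0, averaging 0.50.

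**Several staff per participant (reaches only the staff triggers in 7.4).** Suppose the truth is one rater beside k staff, with balanced margins. With t the staff–truth kappa and s the staff–staff kappa, Fleiss = [2t + (k − 1)s]/(k + 1), and staff–staff pairs are (k − 1)/(k + 1) of all pairs. Set t = 0 (chance accuracy):

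| Staff k | Staff–staff share of pairs | Fleiss if staff fully agree (s = 1) | s needed to reach 0.41 |
|---|---|---|---|
| 2 | 1/3 | 0.33 | not attainable |
| 3 | 1/2 | 0.50 | 0.82 |
| 4 | 3/5 | 0.60 | 0.68 |

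A participant gives one guess against one truth, so k = 1, there are no such pairs, and uninformative guesses give 0.

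**The case against.** **Details such as the coding of 'uncertain' belong in an analysis plan.** Often so, and one may exist. But the statistic, the cut-off and the resulting change of design are fixed in the protocol, which also offers the third answer.

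**The uncertain share is unknown and may be small.** This stands. The crossing is conditional, and the pilot participant value of 0.69 is well above the cut-off.

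**The arm example is extreme.** This also stands. Section 3.2 says guesses used the presence or absence of hyperglycaemia, so both arms may be informed. The example shows what a pooled kappa can hide; it is not a forecast.

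**A reader might infer that the rule can be tripped by staff merely agreeing with one another.** The documents do not support that as a general claim. Section 8.2 describes guess against truth. Fleiss's kappa is a named trigger only in 8.3, for participants, where the problem cannot arise. For 7.4 it needs the truth pooled as one rater, which Table 2 suggests but does not state, and, at chance accuracy, at least three largely concordant staff. The 3 and 4 in Table 2 are maxima, and pilot research midwives collecting outcomes had at most 2 assessors. The pilot values for staff receiving the baby (0.44, up to 3 assessors) and ward staff (0.43, up to 4) lie just above 0.41, but the table cannot show whether that reflects the truth or mutual agreement.

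**A reader might also infer that kappa alone settles whether placebo ends.** It does not. Blinding data are collected only after slow recruitment or a projected budget shortfall, and the Trial Steering Committee acts on them.

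**Conclusion.** The point holds as a poorly suited and under-specified decision rule. It would go too far to call kappa simply the wrong statistic, because for single definite guesses it is a usable measure of agreement with the truth.

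- **Participant rule in 8.3.** Keeping or dropping 'uncertain' moves the same data across 0.41 once the uncertain share reaches about 10% to 34%, for assumed accuracy of 0.75 to 0.95 that is equal in both arms. Below those shares the decision is unaffected.
- **Both sections.** Pooling the arms can reduce complete unblinding of one arm to a kappa of 0.20.
- **Staff triggers in 7.4 only.** If the truth is pooled with the staff, concordant staff at chance accuracy give 0.33, 0.50 and 0.60 with 2, 3 and 4 staff.

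Separately, and without any assumption, 7.4 and 8.3 disagree on whose result triggers the change. The rule should be settled before any blinding data are collected.

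**What to change.** In 7.4, 8.2 and 8.3, replace kappa by Bang's blinding index, reported per arm: correct minus wrong guesses, divided by all asked, with 'uncertain' kept in the denominator. Compare each staff guess with the true allocation only, with standard errors clustered by participant.

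Keep 0.41 as the cut-off for the average of the two arm indices. It carries over because, under 1:1 allocation with no uncertain answers, that average equals Cohen's kappa of guess against truth. If p1 and p2 are the proportions correct in the two arms, the average is [(2p1 − 1) + (2p2 − 1)]/2 = p1 + p2 − 1. Kappa has Po = (p1 + p2)/2 and Pe = 0.5, which gives the same value. The index still falls as uncertain answers increase, but by a rule set in advance.

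Reconcile 7.4 (participants, postnatal clinicians or research staff) with 8.3 (participants only) on whose result triggers the change.

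The cost is a text change and a few lines of code on the same data. The downside is that Table 2 must be re-analysed before the trial can be compared with the pilot.

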8.3 INTERIM ANALYSES

If recruitment falls below 80% of the expected recruitment rate after two consecutive 6 monthly assessments, we will undertake a detailed assessment of research staff at participating sites to understand barriers and facilitators to recruitment. We will also commence the collection of data regarding the ability to maintain blinding for a minimum of 6 months (or until a minimum of 100 participants if fewer than 100 participants have been recruited in 6 months) to undertake an analysis of the potential to maintain blinding. If the blinding of participants indicates that there is at least moderate agreement between the participants prediction of the allocation and their true allocation (Fleiss's Kappa statistic is above 0.41), the Trial steering committee will recommend reverting to an "Open label trial" where the use of placebo is abandoned and

participants will be allocated to either “Open Label Betamethasone” (ie the participant, research staff and clinical staff will be aware of the patients allocation) or “standard care” without the use of either betamethasone or a placebo. An open label trial will allow additional sites to participate and substantially reduce the cost and logistics of the supply of masked betamethasone and normal saline syringes.

There are no other planned interim analyses for this trial. In particular, there will be no interim analyses based on the primary outcome. The Data and Safety Monitoring Committees may recommend an interim analysis if concerns are raised about the safety or benefit to risk profile of the trial.

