Stutchfield et al reported on the behavioural and educational outcomes of a subset of school aged children (aged 8-15) who were involved in the ASTECS trial and showed no statistically significant differences in a range of parental reported indices of child behavioural and emotional health.⁴⁷ However, children exposed to antenatal betamethasone were more likely to be in the lowest quartile of academic ability based on a school assessment. These data must be interpreted with caution due to the low response rate for the overall follow-up study (only 43% of the original cohort of 942). Even fewer were involved in the school-aged assessment (37%). Furthermore, the ASTECS trial was designed as an open label trial and thus there was the potential for bias. Nevertheless, these data highlight the need for further follow-up of children from well conducted, randomised, placebo-controlled trials. Additional concerns have been raised from a large Finnish cohort study (n=670,097) demonstrating increased mental and behavioural issues in children exposed to antenatal corticosteroids born at term (8.9% in exposed children, 6.3% in unexposed children; hazard ratio (HR) 1.47 (95% CI 1.36, 1.60) p<0.001).¹⁷ However, in this registry-based cohort study, the majority of these infants were exposed earlier in pregnancy due to a perceived risk of preterm birth, and not within the seven days prior to birth. Although the authors attempted to adjust for the huge range of confounders in this observational cohort study, it is possible that the steroid

exposed children represent a very different cohort to the unexposed group and that any differences in the childhood outcomes reflect the adverse pregnancy events in the corticosteroid exposed group rather than necessarily a direct effect of corticosteroids.¹⁷ Importantly, there was no significant increase in the rate of severe or profound intellectual disability (HR 1.17; 95% CI 0.37 to 3.69) or even the rates of mild, moderate or unspecified intellectual disability (HR 0.96; 95% CI 0.64 to 1.42) in those exposed to corticosteroids but who were subsequently born at term. The increase in the primary outcome was driven predominantly by an increase in the rates of attention deficit hyperactivity disorder (HR 1.33, 95% CI 1.06 to 1.65, p=0.01), “Other” behavioural and emotional disorders (HR 1.44, 95% CI 1.19 to 1.73, p<0.001), and sleep disorders HR 1.79 (1.31 to 2.44, p<0.001).¹⁷

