We assessed the ability for participants, clinicians and research staff to remain blinded to the treatment allocation⁵² and found that while it was possible for some participants to guess their treatment allocation on the basis of the presence or absence of subsequent maternal hyperglycaemia, this was by no means the case for all participants (Table 2) and did not necessarily correlate with staff providing clinical care correctly guessing the treatment allocation. Both the midwife administering the study medication and the midwife collecting the research outcome data demonstrated the highest likelihood of accurately predicting the treatment allocation. In the former group, this was due to the recognition that even though the syringe was mostly masked with the trial identification label, the cloudy betamethasone suspension could still be distinguished from the clear saline solution in the trial syringes. The research midwives collecting the outcome data were able to correctly predict the treatment allocation on the basis of the presence or absence of maternal hyperglycaemia when the participant blood glucose monitoring logs were collected at the time of CS. While the blinding of participants was less optimal than we had hoped, the fact that clinicians providing postnatal care could remain blinded provides a justification to proceed with a double blinded study since it will be these clinicians who will make the decisions regarding patient care (maternal and neonatal) which form the basis of our primary and key secondary outcomes. We have also identified strategies to improve the syringe masking to ensure that staff administering the study medication would remain blinded. Preventing research midwives from collecting maternal blood sugar data by having participants upload these themselves (direct from their glucometer) will also help to maintain blinding of research personnel involved in the collection of outcome data.

As part of the pilot trial, a qualitative assessment of participant (n=13) and staff perspectives (n=10) of the trial was undertaken. All participants confirmed that they felt very well informed about the trial, found it highly acceptable, and an important topic to study. Likewise, interviews with staff indicated great confidence that the trial benefits outweighed the risks, and that this was an important trial to generate robust evidence to guide practice.

Table 2: Assessment of participant and staff blinding to treatment allocation

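### The rule for abandoning placebo is stated inconsistently in Protocol 7.4, 8.3 and 13.2, and under 8.3 mothers' guesses alone could unblind the clinicians whose decisions make up the primary outcome

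*Protocol*

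**What the plan says.** Two sections of the protocol describe a switch from placebo control to an open-label comparison.

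- **Section 8.3 (Interim Analyses).** The gate is recruitment only: "If recruitment falls below 80% of the expected recruitment rate after two consecutive 6 monthly assessments". Blinding data are then collected for at least 6 months, and until at least 100 participants have been recruited. The test concerns participants: "If the blinding of participants indicates that there is at least moderate agreement between the participants prediction of the allocation and their true allocation", with Fleiss's kappa above 0.41 as the limit. If it is met, "the Trial steering committee will recommend reverting to an" open-label design in which participants, research staff and clinical staff all know the allocation. The section adds that no other interim analysis is planned.
- **Section 7.4 (Trial Risks).** There are two gates: "These data will only be collected in the event of (i) slow recruitment (see Trial Risk 2) or (ii) projected budget shortfalls". The test covers three groups: "if the Kappa statistic for participants, postnatal clinicians or research staff is above 0.41". On the committee's role it says: "The decision to pivot to an open trial will be made by the Trial Steering Committee".

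Section 13.2 (Data Monitoring Committee) states without qualification that the trial will have no interim analyses.

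The pilot account in section 3.2 concedes that participants were less well blinded than hoped. It goes ahead because "the fact that clinicians providing postnatal care could remain blinded provides a justification to proceed with a double blinded study", and explains that these clinicians make the care decisions on which the primary and key secondary outcomes rest. The primary outcome (section 4) is nursery admission plus any respiratory support for 60 minutes or more, including low-flow gas or extra incubator oxygen.

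**The concern.** Three things are wrong together.

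1. The sections disagree on what opens the gate, whose guesses count and what the committee must do. A steering committee facing slow recruitment or a funding gap could reach opposite conclusions depending on which section it reads.
2. The limit of 0.41 lies below the pilot point estimates for the groups it is applied to, so once the gate opens the test is likely to be passed.
3. Under 8.3 the test never consults the people whose blinding the protocol says matters. The protocol tolerates mothers guessing because postnatal clinicians can stay blinded. Section 8.3 then treats mothers guessing as sufficient reason to unblind those clinicians.

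At stake is ascertainment of the primary outcome. Admitting a baby and continuing low-level support past an hour involve clinical judgement, which knowledge of allocation could influence. Outcomes recorded by unblinded staff cannot be repaired afterwards.

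**Working it through.** **Step 1. The rules side by side**

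| Element | 7.4 | 8.3 | 13.2 |
|---|---|---|---|
| Gate | Slow recruitment or budget shortfall | Slow recruitment | – |
| Whose kappa | Participants, postnatal clinicians or research staff | Participants | – |
| Committee role | Decides | Will recommend open label | – |
| Interim analysis | Blinding data analysed before trial completion | This one only | None |

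Hypothetical cases where the sections diverge, with the recruitment gate open unless stated:
- Participants 0.35, research staff 0.60: 7.4 is met, 8.3 is not.
- Participants 0.60, clinicians 0.20: 8.3 directs a recommendation to go open label; 7.4 leaves it to the committee.
- Budget shortfall with recruitment on target: 7.4 opens the gate, 8.3 does not.

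**Step 2. Pilot values against 0.41** (section 3.2, Table 2)

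| Group | n | Kappa | 95% CI | Above 0.41 |
|---|---|---|---|---|
| Participants | 47 | 0.69 | 0.39 to 0.98 | yes |
| Doctor performing CS | 26 | 0.24 | -0.22 to 0.71 | no |
| Staff receiving baby | 32 | 0.44 | 0.09 to 0.80 | yes |
| Endocrinologist | 33 | 0.33 | -0.01 to 0.67 | no |
| Ward midwife or doctor | 15 | 0.43 | -0.10 to 0.96 | yes |
| Research midwife | 45 | 0.81 | 0.54 to 1.00 | yes |
| Midwife giving or checking drug | 41 | 0.84 | 0.68 to 1.00 | yes |

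Five of seven point estimates exceed 0.41, including at least one in each category 7.4 names. The raw guesses are not given, so the kappas cannot be recomputed and are taken as stated.

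**Step 3. Chance that the participant estimate crosses 0.41 at the minimum of 100**

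Standard error from the pilot interval: (0.98 − 0.39) / 3.92 = 0.151 at n = 47. Scaled to n = 100: 0.151 × √(47/100) = 0.103. With a normal approximation, P(cross) = Φ((κ − 0.41) / 0.103):

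| True κ | P(cross) |
|---|---|
| 0.30 | 14% |
| 0.39 (pilot lower limit) | 42% |
| 0.50 | 81% |
| 0.60 | 97% |
| 0.69 (pilot estimate) | 99.7% |

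**Step 4. What unblinding could do (illustration; the shifts are assumed)**

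The design figure reproduces: 6% against 3%, 90% power, two-sided 0.05 and continuity correction give 1068 per arm, or 1102 after 3% drop-out, against 1100 stated. Analysed per arm: 1100 × 0.97 = 1067.

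Suppose there is no true effect and 6% of controls have the outcome. If knowing the allocation lowered the recorded betamethasone rate across the whole trial to 5.5%, 5.0% or 4.5%, the chance of a false significant benefit would be about 7%, 17% or 34%, against 2.5% nominal in that direction. A blinded first phase dilutes this: if half the participants were open label and their recorded rate were 5.0%, the overall rate would be (6.0 + 5.0) / 2 = 5.5%, the 7% case.

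**The case against.** The strongest reply is that this is a disclosed, prespecified contingency to keep the trial viable, and that several gates stand before it. Under 8.3 there must be two consecutive six-monthly shortfalls, an assessment of recruitment barriers and at least 6 further months of blinding data. Taking the first review at month 6, that is 2 × 6 + 6 = 18 months at the earliest. Section 7.4 speaks of the committee considering the analysis, and in the budget case of it possibly requesting one. This stands: the rule may never be used, and kappa alone does not set it off. A reader might infer that the switch is automatic once the gate opens. The text does not support that; only the wording in 8.3 on recommending open label is directive.

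A reader might also infer from the pilot that the test cannot discriminate. It can: the chance of crossing runs from 14% at a true kappa of 0.30 to 99.7% at 0.69. The participant interval (0.39 to 0.98) includes 0.41, and the ward-staff value rests on 15 participants, so "already exceeded" is true of point estimates only. Section 3.2 does link participants' guesses to hyperglycaemia, which neither masked syringes nor self-uploaded glucose readings would remove, but it says this of some participants and does not make it the only cue.

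It is tempting to read section 8.2 as pooling the blinded and open phases inseparably. Section 8.2 does not mention phases, a pivot would have a date, and analysis by phase can be left to the SAP. Likewise, the remark that "the ASTECS trial was designed as an open label trial and thus there was the potential for bias" qualifies that trial's school-age follow-up. It shows that the protocol recognises the hazard, but does not criticise the neonatal result behind the assumed effect size.

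Section 7.4 adds that later childhood outcomes would be assessed blind. That does not protect this trial's primary outcome, and sections 3.4 and 7.1 leave the childhood outcomes to future studies.

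**Conclusion.** The point holds as a should-fix. The conflict between 7.4, 8.3 and 13.2 is on the face of the text and depends on no assumption. The mismatch between the 8.3 trigger and the section 3.2 rationale is equally plain: 8.3 could take the trial open label on mothers' guesses while the clinicians who decide nursery admission and respiratory support remain well blinded.

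The likelihood of a crossing depends on the main-trial participant kappa resembling the pilot's and on a normal approximation with the pilot-based standard error. On that basis it is likely (99.7% at 0.69, 81% at 0.50) but not certain (42% at 0.39). The size and direction of any resulting bias are unknown; the false-benefit figures show only how sensitive the trial would be to an assumed shift. The contingent nature of the rule keeps this below must-fix.

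**What to change.** - **One rule.** State it identically in 7.4 and 8.3, with the same gate, group and committee role, and amend 13.2 to acknowledge the blinding analysis as the one planned exception.
- **Trigger group.** Base it on the staff who decide nursery admission and respiratory support. Guesses by participants or research staff alone should not suffice.
- **Criterion.** Judge a confidence limit of the agreement index against a preset value, not a point estimate. The pilot interval for ward staff (-0.10 to 0.96) shows how little a small sample settles.
- **After a pivot.** Withhold allocation from the neonatal team and the outcome abstractor as far as practicable, and report the blinded-phase estimate beside the overall one.

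The cost is amendment wording and one additional reported estimate. The real downside is that a switch intended to save money and admit more sites becomes harder to invoke, and keeping the neonatal team unaware in an open-label phase may be only partly achievable.
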